TAF	Tenofovir alafenamide fumarate
TDF	Tenofovir disoproxil fumarate
TFLs	Tables, figures, and listings
WHO	World Health Organization

1. INTRODUCTION

This was a post-authorization randomized open-label study comparing the bone and renal safety profiles of adolescents (12-17 years, inclusive) with chronic hepatitis B (CHB) infection. The study assigns patients receiving TDF 245mg by mouth (per os[PO]) once daily for the treatment of CHB to one of two schedules for bone and renal laboratory monitoring and bone mineral density (BMD) measurements over 96 weeks. The study population was enrolled through one of the 23 participating European clinics (ie., Belgium, Romania, Spain, Bulgaria, France, Italy, Greece, and the United Kingdom) and FPFV was in July 2015.

The scope of this statistical analysis plan (SAP) is for the final analysis (Week 96).

1.1. Study Objectives

Primary Study Objectives
	
To characterize the long term (i.e., 96 weeks of follow up) bone safety profile of open-label TDF treatment in adolescents with CHB. This includes prospectively evaluating and comparing the bone mineral density (BMD) changes between CHB- infected adolescents 12 to < 18 years of age treated with TDF in European treatment centers who were assigned to one of two schedules for renal and bone laboratory monitoring and BMD measurements. Primary study endpoint was the percent changes in BMD from Baseline through study Week 96.

Secondary Study Objectives
	
 • To document all serious adverse drug reactions (SADR) and all renal- and bone-related adverse events (AEs), including renal and bone laboratory abnormalities • To determine the time to diagnosis of renal and bone AEs and document the resulting patient management and outcome(s) • To assess the clinical management and outcomes of renal- and bone-related \geq Grade 3 laboratory parameters and clinical SAEs. • To assess the efficacy and tolerability of TDF in adolescents with CHB infection • To assess the use of oral vitamin D, calcium and phosphate supplementation and explore the association between supplement use and rates of bone and renal AEs • To describe the demographics and disease characteristics of adolescents with CHB infection treated with TDF.

1.2. Study Design

Design Configuration and Subject Population
	
This study is a post-authorization, randomized open-label study comprised of adolescents who initiate 245mg PO once daily tTDF therapy for the treatment of HBV in clinical sites across Europe. The subjects will be assigned in a 1:1 ratio to one of two monitoring groups using a validated computer-generated tool for randomization. Subjects will be assigned to Group 1 or 2 upon enrollment into the study but prior to Baseline laboratory and DXA imaging assessments.

Treatment Groups
	
Monitoring Group 1 will receive tTDF 245mg PO once daily for the treatment of CHB infection, followed over 96 weeks using an enhanced monitoring protocol which includes more frequent laboratory bone biomarker testing and lumbar spine and whole-body DXA scans (Baseline, and Weeks 24, 48, 72, 96) than that which is specified for Group 2. With the exception of an enhanced monitoring protocol for bone and renal outcomes, subjects will be managed according to local standards of care.
 
Monitoring Group 2 will be the comparator group of subjects receiving tTDF 245mg PO once daily for the treatment of CHB infection, and with the exception of pre-specified bone monitoring, will be managed according to local standards of care. Group 2 will receive serum bone biomarker testing, and lumbar spine and whole body DXA at Baseline, Weeks 48 and 96.

Key Eligibility Criteria
	
Inclusion Criteria
 
 • Subjects must meet all inclusion criteria as stated in the protocol to be eligible for participation in this study. These include: 
 — 12 to <16 years of age — Documented chronic HBV infection (e.g. positive serum HBsAg\geq 6 months) — Weight \geq 35 kg — Able to swallow oral tablets — Negative serum β-HCG pregnancy test — Estimated glomerular filtration rate (creatinine clearance) \geq 80 mL/min/1.73m²

	
Estimated creatinine clearance using Schwartz Formula: $(\text{mL}/\text{min}/1.73\text{m}^2) = k \times L/\text{Scr}$ [k is a proportionality constant: for adolescent females ≥ 12 years old, $k = 0.55$, and for adolescent males ≥ 12 years, $k = 0.70$]; L is height in centimeters (cm); and Scr is serum creatinine (mg/dL)]
 
Parent or legal guardian of potential study subjects able to provide written informed consent prior to any screening evaluations and willing to comply with study requirements or subject able to provide written assent as determined by IEC/local requirements and at the Investigator's discretion.

Key Eligibility Criteria
	
Exclusion Criteria
 
Prior therapy with tTDF; subjects may have received prior interferon or oral anti-HBV nucleoside/nucleotide therapy (subjects experienced on interferon must have discontinued therapy for a minimum of six months; treatment-experienced subjects receiving oral anti-HBV nucleoside/ nucleotide treatment at screening should continue their current treatment regimen until tTDF is initiated (i.e., to prevent ALT flare)
 
Sexually-active males or females of reproductive potential who are not willing to use an effective method of contraception during the study.
 
Females who are pregnant or breastfeeding, or females who wish to become pregnant during the course of the study.
 
Known hypersensitivity to tTDF, the metabolites or formulation excipients
 
Any condition (including alcohol or substance abuse) or prior therapy that, in the opinion of the Investigator, would make the subject unsuitable for the study or unable to comply with treatment requirements

Study Periods/Phases
	
Screening period = 30 days
 
Total treatment period = 96 weeks

Randomization, Blinding, and Unblinding
	
 • 30 TDF-naïve subjects were randomized in a 1:1 ratio to receive tTDF 245mg PO daily and assigned to one of two safety monitoring groups (15 subjects each). • Randomization was not stratified by age or region. A centralized randomization procedure was used, whereby numbered bottles of TDF are assigned to subjects via an interactive voice response system (IVRS) according to the randomization code.

Study Duration
	
Subjects will be treated with TDF for 96 weeks. The duration for a given subject is at least 96 weeks plus 30 days to observe safety outcomes.
 
Subjects who permanently discontinue TDF will be asked to return for an end-of-treatment visit within 72 hours of the last dose of TDF. Subjects who permanently discontinue TDF will be followed for 24 weeks off treatment or up to initiation of active treatment, whichever occurs first.

1.3. End of Study

The end of study is defined as the completion of TDF therapy and close-out monitoring by the last enrolled subject (e.g., last enrolled subject completes 96 Weeks of treatment and monitoring).

Randomization
	
Approximately 100 TDF-naïve patients were planned to be randomized in a 1:1 ratio to receive treatment with TDF and assigned to one of two monitoring groups (50 in each group was planned). The subjects were assigned to one of two monitoring groups using a validated computer-generated tool for randomization (dynamic block assignment by site to ensure there are at least 4 subjects randomized per site). Subjects were assigned to Group 1 or 2 upon enrollment into the study but prior to Baseline laboratory and DXA imaging assessments.
 
The study population was enrolled through one of 23 participating European clinics across several countries (eg., Bulgaria, Poland, Romania, Italy, France, Spain, and the United Kingdom) commencing June 2015

-----------------------------	---

Site and/or Stratum Enrollment Limits	There were no enrollment limits imposed at the sites.
Study Duration	
Subjects will be treated with TDF for 96 weeks. The planned duration in-study for a given subject is at least 2 years. TDF is currently approved for use in patients across all specified study countries with participating study clinics aged 12 years of age and up.
 
Subjects who permanently discontinue TDF will be asked to return for an end-of-treatment visit within 72 hours of the last dose of TDF. Subjects who permanently discontinue TDF will be followed for 24 weeks off treatment or up to initiation of active treatment, whichever occurs first.

1.4. Sample Size and Power

Planned Sample Size	100 subjects (50 subjects to one of two monitoring groups)
Power Statement	
The study employed two monitoring protocols which specified the same laboratory and imaging tests for bone and renal markers and differed in the frequency of testing. Group 1 receives more frequent monitoring which is protocol-defined or SmPC specified, and Group 2 subjects are monitored according to a less frequent DXA schedule for BMD and followed the local standard of care for renal monitoring. It is hypothesized (H_0) that there would have been no difference in the timing, management, or subject outcomes resulting from renal or bone AEs among the two monitoring regimens. With a one-tailed test of $\alpha=0.05$, and assuming a non-inferiority margin of 0.10, the study had at least 80% power to detect a difference between the monitoring regimens beyond the specified margin of non-inferiority.
 
The primary safety endpoint is cumulative incidence of at least a 4% decrease from study baseline (BL) in spine bone mineral density (BMD) through Week 96.
 
The null hypothesis is the difference (Group 1 – Group 2) is equal to 0.
 
The alternative hypothesis is the difference (Group 1 – Group 2) is not equal to 0.

Actual Enrollment and Impact on Power	
The study failed to achieve its targeted enrollment of 100 patients, 50 per monitoring group. The study was discontinued as a result of the recent approval of Tenofovir alafenamide fumarate (TAF) medicine which offers a safer treatment option for CHB patients and due to low subject enrollment after the CHMPs assessment of the 18 month interim enrollment report. At the time of its closure the study enrolled 30 patients, 15 per monitoring group. The total enrolled subjects are underpowered to statistically detect differences in outcomes between monitoring groups.

--	--

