300mg oral Tenofovir disoproxil fumarate (Tenofovir DF), which is equivalent to 245mg Tenofovir disoproxil, following enhanced patient monitoring protocol for bone and renal biomarkers

Reference Therapy,
Dose, and Mode of
Administration:

300mg oral Tenofovir DF following local standards of care for patient monitoring for renal biomarkers

Criteria for Evaluation:

Safety:

The primary safety endpoint is the indication of a cumulative incidence of a $\geq 4\%$ decrease from Baseline BMD of the spine or whole body through Week 96. Secondary endpoints include bone and renal AEs. Bone AEs may include reports of bone pain or fractures. Renal AEs may include reductions in creatinine clearance, and clinical and laboratory evidence of Grade 3 or greater renal tubulopathy or toxicity (e.g. proximal renal tubulopathy, Fanconi syndrome).

Bone and renal AEs, concomitant medications (including dietary supplements) and specified clinical laboratory tests will be collected each time subjects from Group 1 or Group 2 return for scheduled monitoring by the study site over a 96 week period.

Efficacy:

An efficacy analysis will be conducted after the last assigned subject reaches Week 96. The analysis will evaluate the difference in the proportion of subjects (Group 1 and 2 data will be pooled, as subjects have exposure to a single mode of therapy) achieving a composite endpoint of HBV DNA < 400 copies/mL and ALT normal at Week 96.

Pharmacokinetics: Not applicable

Statistical Methods:

The primary safety analysis will be performed after the last subject reaches Week 96 on Tenofovir DF treatment among both monitoring groups. The primary analysis will evaluate quantitative reductions in spine or whole body BMD compared to baseline assessments through DEXA scanning. A key secondary study objective is to assess within-group and between-group differences in renal biomarker changes (e.g., creatinine clearance using the Schwartz formula, glucosuria, proteinuria) suggestive of renal toxicity. To evaluate the time to detection of renal or bone AEs among the assigned monitoring groups, estimations of incidence rates (events over person time on Tenofovir DF) and time to event analysis will be determined. The evaluation of other clinically relevant endpoints such as sustained virologic response, serologic status, and development of Tenofovir DF resistance will also be assessed as secondary study outcomes for each monitoring group and as a combined cohort.

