Recent data from the GS-EU-174-0115 trial reported HBV DNA lower than 400 copies/mL in 88.5% of Tenofovir DF receiving patients after 72 weeks of treatment. At this same study milestone, no subjects met the primary safety endpoint of a 6% decrease in lumbar spine BMD. As expected for an adolescent population, both treatment arms experienced an overall increase in mean spine BMD. The mean (SD) change in lumbar spine BMD Z-score from baseline to Week 72 in the Tenofovir DF arm was -0.05 (0.310). The mean (SD) change in lumbar spine BMD Z score in the placebo arm was 0.07 (0.377). The mean change in whole body BMD Z score in the Tenofovir DF arm was -0.15 (0.379). The mean change in whole body BMD Z-score in the placebo arm was 0.06 (0.361). Using age and gender matched cohorts, the magnitude of the effect of Tenofovir DF on lumbar spine and whole body BMD also does not appear to be clinically relevant.

The mean (SD) change in creatinine from baseline to Week 72 was 0.1 (0.10) for the Tenofovir DF group and 0.1 (0.09) for the placebo group. No subject had a confirmed increase from the baseline serum creatinine concentration of at least 0.5 mg/dL, a confirmed creatinine clearance rate of < 50 mL/min, or a confirmed serum phosphorus concentration < 2 mg/dL. This study will continue to follow subjects to Week 192.

Two open-label, single-arm, single-center clinical studies have been performed to evaluate the safety and pharmacokinetics of Tenofovir DF in a small number of HIV-1-infected children. Studies 926 and 927 were 96 Week pharmacokinetic and safety studies, which enrolled treatment-experienced children with advanced HIV disease. All subjects received open-label Tenofovir DF as a component of a new antiretroviral regimen.

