8.1.2. Primary Endpoint

The primary endpoint of this study is:

- The identification of bone AEs occurring in subjects taking Tenofovir DF between Baseline and Week 96 of treatment, including the identification of $\geq 4\%$ percent reduction in BMD within subjects and between monitoring groups from Baseline.

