8.6.4. Other Safety Evaluations: Analyses of BMD

Cumulative incidence of at least a 4% decrease from baseline in BMD (spine BMD and whole body BMD) using time-to-event methodology will be summarized and compared between treatment groups using 95% confidence intervals for difference in person time rates.

The percent change from baseline in BMD (spine BMD and whole body BMD) will be summarized over time and compared between treatment groups using the Generalized Linear Model. Lumbar spine and whole body z-scores (derived from DEXA-derived BMD assessments) and the changes in z-scores from Baseline will be summarized.

BMD (via DEXA scan) and serum bone biochemical markers will be summarized over time. Changes from study baseline in bone biochemical markers will also be summarized after adjusting for potential confounders such as age and gender..

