7.3. Bone Mineral Density and Bone Biochemical Markers

BMD primary endpoints to be evaluated include:

- Cumulative incidence of at least a 4% decrease from baseline in spine BMD
- Spine BMD (g/cm^2) and change from baseline
- Percent change from baseline in spine BMD (categorical)
- Z-Scores for spine BMD (g/cm^2) and change from baseline (categorical)
- Cumulative incidence of at least a 4% decrease from baseline in whole-body BMD
- Whole-body BMD (g/cm^2) and change from baseline
- Percent change from Baseline in whole-body BMD (categorical)
- Z-Scores for whole-body BMD (g/cm^2) and change from baseline (Categorical)

Cumulative incidence of at least a 4% decrease from BL in spine and whole-body BMD will be summarized by monitoring group and study week for each randomization age group (12-14 years, 15-17 years). No inferential statistics will be computed.

The percent change from BL in spine BMD and in whole-body BMD will also be summarized categorically by monitoring group and overall for each study week using the following categories: ≤ -4 , > -4 to ≤ -2 , > -2 to ≤ 0 , > 0 to ≤ 2 , > 2 to ≤ 4 , > 4 , and Missing. No inferential statistics will be computed.

Z-score and changes from BL in z-score will also be summarized categorically (n, mean, standard deviation, median, Q1, Q3, minimum and maximum) by monitoring group and overall for each study week. No inferential statistics will be computed.

Spine BMD and whole-body BMD clinical status will also be summarized categorically by monitoring group and overall for each study week using the following categories: > -1 , -1 to -2 , < -2 , Total, and Missing. No inferential statistics will be computed.

Serum bone biochemical markers will be summarized (n, mean, standard deviation, median, Q1, Q3, minimum and maximum) by monitoring group and overall for each study week, as well as the changes from BL. In all cases of serum bone biochemical markers, no inferential statistics will be computed.

The following bone biochemical markers as previously mentioned in the laboratory results section will be assessed:

- N-telopeptide (nmol BCE/L)
- C-telopeptide (ng/mL)
- Serum osteocalcin (ng/mL)

- Bone-specific alkaline phosphatase ($\mu\text{g/L}$)
- Serum PTH (pg/mL)
- Vitamin D (25-hydroxy, [ng/mL])

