7.8. Changes From Protocol-Specified Safety Analyses

No alterations to the protocol-specified safety analysis have been made. The study has been canceled due to low enrolment and due to the approval of TAF for HBV in adolescents in November 2016 as a safer treatment option for patients. With two subjects completing 96 weeks of treatment the safety analysis will shift to focus on subjects' available treatment exposure to TDF.

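### SAP 1.4 names a spine-only primary safety endpoint, in conflict with the protocol synopsis and SAP 7.3, and no planned output counts a ≥4% loss at either site

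*SAP*

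**What the plan says.** The documents describe the ≥4% BMD endpoint in several places.

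- **Protocol synopsis, Criteria for Evaluation (Safety):** the primary safety endpoint is the cumulative incidence of a ≥4% "decrease from Baseline BMD of the spine or whole body through Week 96". The synopsis paragraph on statistical methods also names both sites, joined by *or*, for the primary analysis.
- **Protocol 3.1 and 8.1.2:** the primary endpoint is bone adverse events, including a ≥4% "reduction in BMD within subjects and between monitoring groups from Baseline" (wording of 8.1.2). No site is named.
- **Protocol 8.6.4:** "Cumulative incidence of at least a 4% decrease from baseline in BMD (spine BMD and whole body BMD) using time-to-event methodology" is to be summarized and compared between groups.
- **SAP 1.4:** "The primary safety endpoint is cumulative incidence of at least a 4% decrease from study baseline (BL) in spine bone mineral density", through Week 96. Only the spine is named.
- **SAP 7.3:** under "BMD primary endpoints to be evaluated include" there are eight items, four per site. They include "Cumulative incidence of at least a 4% decrease from baseline in whole-body BMD" and the matching spine item.
- **SAP Appendix 3:** Tables 26.1 to 26.3 cover the spine and Tables 27.1 to 27.3 the whole body. No table combines the sites.
- **SAP 7.8:** "No alterations to the protocol-specified safety analysis have been made".

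**The concern.** The primary safety endpoint has one site in SAP 1.4, two parallel sites in SAP 7.3, and two sites joined by *or* in the synopsis. A reader of the study report cannot tell which figure is the primary result, and SAP 7.8 gives no sign that anything differs from the protocol.

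In a descriptive report the definition of what was counted is most of the result. Few events are expected, so one or two subjects decide the figure.

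The conflict also reaches an actual output. SAP 4.2 puts the last non-missing primary and key secondary endpoint values into the listing of premature discontinuations. Only two of 30 subjects completed 96 weeks (SAP 1.4 and 2.1), so that listing may cover as many as 30 − 2 = 28 subjects. Under SAP 1.4 its primary value would be spine BMD alone; under SAP 7.3 it would be both sites.

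**Working it through.** **1. The plan's own figure.** The one performance figure in SAP 1.4 is power of at least 80% (one-sided α = 0.05, margin 0.10, 50 per group). For a common event rate p, power = Φ(0.10 / √(2p(1−p)/50) − 1.645). This gives 84.2% at p = 3.7%, 80.2% at 4.2% and 68.9% at 5.8%, so the statement holds for p up to about 4.2%. The documents attach no event rate and no BMD site to it. It therefore can be neither reproduced nor used to tell which site was meant.

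**2. The definitions side by side.**

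| Place | Site(s) for the ≥4% decrease | Status given |
|---|---|---|
| Protocol synopsis | spine *or* whole body | primary safety endpoint |
| Protocol 3.1, 8.1.2 | none named | part of the primary endpoint |
| Protocol 8.6.4 | spine *and* whole body | planned BMD analysis |
| SAP 1.4 | spine | primary safety endpoint |
| SAP 7.3 | spine; whole body | both headed primary |
| SAP 7.8 | – | no change declared |

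No protocol section restricts this study's endpoint to the spine. On site coverage, SAP 7.3 agrees with protocol 8.6.4, and SAP 1.4 is the outlier.

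**3. Can the either-site count be recovered from the planned tables?** Let a be the number of subjects in a group of n with a ≥4% loss at the spine, and b the number at the whole body. Then

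max(a, b) ≤ either-site count ≤ min(n, a + b).

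With a = b = 1 and n = 15, the count is 1 (same subject) or 2 (different subjects), that is 1/15 = 6.7% or 2/15 = 13.3%. Tables 26.1 and 27.1 cannot separate these.

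**4. Can it be recovered from listings?** Among Listings 1 to 19 in SAP Appendix 3, none is for post-baseline BMD, although protocol 8.2 says individual data will be listed. The SAP 4.2 listing carries only the most recent value, so it would miss an earlier ≥4% loss that had recovered.

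**5. Background on the two sites (means only).** Protocol 1.2.3.1 gives Week 72 changes in Z-score from the earlier placebo-controlled adolescent trial. I assume that all 52 and 54 randomized subjects contributed and that the bracketed values are standard deviations.

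- Spine: −0.05 − 0.07 = −0.12; SE = √(0.310²/52 + 0.377²/54) = 0.067; 95% CI −0.25 to +0.01.
- Whole body: −0.15 − 0.06 = −0.21; SE = √(0.379²/52 + 0.361²/54) = 0.072; 95% CI −0.35 to −0.07.

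The difference from placebo in mean Z-score was larger at the whole body, but the intervals overlap widely. This gives a reason not to relegate the whole body without comment. It says nothing direct about the ≥4% threshold.

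**The case against.** The strongest reply is that SAP 1.4 contains one stray sentence in a sample-size section. The section and tables that govern the analysis keep both sites under a primary heading. Protocol 8.6.4 reads naturally as one incidence per site, which SAP 7.3 delivers. The earlier adolescent trial also treated the sites as separate endpoints, spine primary and whole body secondary (protocol 1.2.3.1). SAP 7.3 plans no inferential statistics on this incidence, so no test or decision depends on the site named in 1.4.

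Much of this stands, and it rules out four stronger readings that a reader might infer:

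- *That the whole body has been dropped.* It has not: SAP 7.3 and Tables 27.1 to 27.3 report it.
- *That the protocol's endpoint is never computed.* This follows only if the synopsis *or* means that a subject counts once for a loss at either site. That is its plain reading, but no section spells it out and 8.6.4 can be read site by site.
- *That a spine-only figure could be as little as half the either-site figure.* This needs the 5.8% in protocol 8.9 to apply at each site with no overlap (5.8% + 5.8% = 11.6%). The protocol does not say which site the 5.8% refers to. If it is already an either-site rate, nothing changes.
- *That SAP 1.4 keeps the site less likely to reach a 4% loss.* The documents give no ≥4% incidence by site; the Z-score contrast concerns means.

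The reply does not reconcile SAP 1.4 with the synopsis or with SAP 7.3. Nor does it make the SAP 7.8 statement accurate for 1.4 as written, or supply an either-site count.

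**Conclusion.** The point holds as an inconsistency in the definition of the primary safety endpoint, together with a missing summary. SAP 1.4 departs from the synopsis and from SAP 7.3, and SAP 7.8 does not disclose it. On the plain reading of the synopsis, its endpoint has no planned output and can only be bounded from the two marginal tables.

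The size is modest. Both sites are reported, the incidence is summarized descriptively, and the study closed with 15 subjects per group. SAP 1.4 itself says the enrolled number is underpowered for group differences. The likely effect is a discrepancy of a subject or so in what is called the primary count. It should be corrected before reporting, but it does not threaten the study's conclusions. The judgment that an output is missing rests on reading *or* as a per-subject, either-site count; the conflict between SAP 1.4 and 7.3 does not depend on that reading.

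**What to change.** 1. In SAP 1.4 and 7.3, state one primary definition that matches the synopsis: first decrease of at least 4% from baseline in BMD at the spine or the whole body, through Week 96.
2. Add one either-site row or table, by monitoring group and pooled, ahead of Tables 26.1 and 27.1. Keep those two as components.
3. If spine only is intended, say so in SAP 7.8 as a change to the primary endpoint, give the reason, and change the heading of the SAP 7.3 list accordingly.
4. Make the SAP 4.2 discontinuation listing follow whichever definition is adopted.

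The cost is SAP wording, one derived variable and one table row, all from DXA data already collected.
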